8.2. Subject Inclusion Criteria

1. Definite or probable PBC diagnosis (consistent with AASLD and EASL practice guidelines; [Lindor 2009](#); [EASL 2009](#)), as demonstrated by the presence of ≥ 2 of the following 3 diagnostic factors:
 - History of elevated ALP levels for at least 6 months.
 - Positive antimitochondrial antibody (AMA) titer or if AMA negative or in low titer ($<1:80$) PBC-specific antibodies (anti-GP210 and/or anti-SP100 and/or antibodies against the major M2 components [PDC-E2, 2-oxo-glutaric acid dehydrogenase complex]).
 - Liver biopsy consistent with PBC.
2. A mean total bilirubin $>ULN$ and $\leq 3 \times ULN$ and/or a mean ALP $>5 \times ULN$
3. Age ≥ 18 years
4. Either is not taking UDCA (no UDCA dose in the past 3 months) or has been taking UDCA for at least 12 months with a stable dose for ≥ 3 months prior to Day 0.
5. Contraception: Female subjects must be postmenopausal, surgically sterile, or if premenopausal (and not surgically sterile), be prepared to use ≥ 1 effective method of contraception during the study and for 30 days after the end of treatment visit. Effective methods of contraception are considered to be those listed below:
 - Double-barrier method, ie, (a) condom (male or female) or (b) diaphragm, with spermicide; or

- Intrauterine device (IUD); or
 - Vasectomy (partner), or
 - Hormonal (eg, contraceptive pill, patch, intramuscular implant or injection, or
 - Abstinence, if in line with the preferred and usual lifestyle of the subject)
6. Must provide written informed consent and agree to comply with the study protocol

8.3. Subject Exclusion Criteria

1. History or presence of other concomitant liver diseases including:
 - Hepatitis C virus infection
 - Active hepatitis B infection; however, subjects who have seroconverted (hepatitis B surface antigen and hepatitis B e antigen negative) may be included in this study after consultation with the medical monitor.
 - Primary sclerosing cholangitis
 - Alcoholic liver disease
 - Definite autoimmune liver disease or overlap hepatitis
 - Nonalcoholic steatohepatitis
 - Gilbert's Syndrome
2. Presence of clinical complications of PBC or clinically significant hepatic decompensation, including:
 - History of liver transplant, current placement on a liver transplant list, or current MELD score >12. Subjects who are placed on a transplant list despite a relatively early disease stage (for example per regional guidelines) may be eligible as long as they do not meet any of the other exclusion criteria.
 - Cirrhosis with complications, including history (within the past 12 months) or presence of:
 - Variceal bleed
 - Uncontrolled ascites
 - Encephalopathy
 - Spontaneous bacterial peritonitis
 - Known or suspected hepatocellular carcinoma
 - Prior transjugular intrahepatic portosystemic shunt procedure
 - Hepatorenal syndrome (type I or II) or Screening (visit 1 or 2) serum creatinine >2 mg/dL (178 µmol/L)
3. Mean total bilirubin >3× ULN

4. Subjects who have undergone gastric bypass procedures (gastric lap band is acceptable) or ileal resection or plan to undergo either of these procedures.
5. Other medical conditions that may diminish life expectancy, including known cancers (except carcinomas *in situ* or other stable, relatively benign conditions such as chronic lymphatic leukemia).
6. If female: plans to become pregnant, known pregnancy or a positive urine pregnancy test (confirmed by a positive serum pregnancy test by the central laboratory), or lactating.
7. Known history of human immunodeficiency virus infection.
8. Medical conditions that may cause non-hepatic increases in ALP (eg, Paget's disease or fractures within 3 months).
9. Other clinically significant medical conditions that are not well controlled or for which medication needs are anticipated to change during the study.
10. History of alcohol abuse or other substance abuse within 1 year prior to Day 0.
11. Participation in another investigational product, biologic, or medical device study within 30 days prior to Screening. Participation in a previous study of OCA is allowed with 3 months washout prior to enrollment in this study.
12. Mental instability or incompetence, such that the validity of informed consent or ability to be compliant with the study is uncertain.
13. History of known or suspected clinically significant hypersensitivity to OCA or any of its components.
14. UDCA naïve (unless contraindicated)

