 6. If female: plans to become pregnant, known pregnancy or a positive urine pregnancy test (confirmed by a positive serum pregnancy test), or lactating
 7. Known history of human immunodeficiency virus infection
 8. Medical conditions that may cause nonhepatic increases in ALP (eg, Paget's disease or fractures within 3 months)
 9. Other clinically significant medical conditions that are not well controlled or for which medication needs are anticipated to change during the study
 10. History of alcohol abuse or other substance abuse within 1 year prior to Day 0
 11. Participation in another investigational product, biologic, or medical device study within 30 days prior to Screening. Participation in a previous study of OCA is allowed with 3-month washout prior to enrollment in this study
 12. Mental instability or incompetence, such that the validity of informed consent or ability to be compliant with the study is uncertain
 13. History of known or suspected clinically significant hypersensitivity to OCA or any of its components
 14. UDCA naïve (unless contraindicated)

Investigational Product, Dosage and Mode of Administration:

OCA (5 mg or 10 mg tablets)

Placebo (matching tablets)

Duration of Treatment:

It is estimated that subjects will be followed up for a minimum of 6 years. The study is event driven and total duration of treatment will be determined by the time to accrue 121 total primary endpoint events.

Duration of Subject Participation:

It is estimated that subject participation will be a minimum of approximately 6 years.

Criteria for Evaluation:

Primary Objectives	Assessments
Clinical outcomes	
 • Death (all-cause) • Liver transplant • MELD score ≥ 15 • Hospitalization (as defined by a stay of 24 hours or greater) for new onset or recurrence of: 
 – Variceal bleed – Encephalopathy (as defined by a West Haven score of ≥ 2) – Spontaneous bacterial peritonitis (confirmed by diagnostic paracentesis) • Uncontrolled ascites (diuretic resistant ascites requiring therapeutic paracentesis at a frequency of at least twice in a month) • Hepatocellular carcinoma confirmed by 2 complimentary imaging modalities
Secondary Objectives	
Individual components of the primary endpoint	As listed above and including liver-related death
Change in baseline liver biochemistry	Liver biochemistry (see Table 10 : for list of analytes to be tested)

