5. INTRODUCTION

5.1. Overview of Primary Biliary Cirrhosis and Obeticholic Acid

Primary biliary cholangitis, (PBC, also known as primary biliary cirrhosis) is a serious, life-threatening, cholestatic liver disease of unknown etiology that, without treatment, frequently progresses to hepatic fibrosis and eventual cirrhosis, hepatic decompensation, and necessitates liver transplantation or results in death. PBC is a rare disease with reported prevalence in the US of 40.2/100,000 (Kim 2000). PBC disproportionately affects women approximately 10:1 and is typically diagnosed in patients between 40 to 60 years of age.

Ursodeoxycholic acid (UDCA), a physiological constituent of human bile, is currently the only treatment approved for PBC (Lindor 2009). While UDCA therapy has a marked effect on the treatment of PBC, up to 50% of patients show a suboptimal response or no response to UDCA. Such patients are at significantly increased risk of a poor clinical outcome due to PBC disease progression. There is a clear unmet medical need for better therapies for patients with PBC that have an inadequate response to UDCA, or those who cannot tolerate UDCA (typically due to gastrointestinal adverse events [AEs]). Obeticholic acid (OCA) is being developed for the treatment of PBC and to provide patients that have an inadequate response to or poor tolerance of UDCA a novel treatment option that is safe and effective.

OCA is a modified bile acid and farnesoid X receptor (FXR) agonist that is derived from the primary human bile acid chenodeoxycholic acid (CDCA). OCA is currently being developed in the United States (US) and Europe for the treatment of PBC and other chronic liver diseases. OCA has been granted Orphan Drug Designation in the US (09 Apr 2008) and Orphan Medicinal Product Designation in the European Union (EU) (27 Jul 2010) for the treatment of PBC. The United States Food and Drug Administration (FDA) has granted accelerated approval for Ocaliva for the treatment of PBC. Ocaliva is not yet approved outside the United States for use in any indication.

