9.2. Concomitant Medications

Concomitant medications (other than prohibited concomitant medications listed in Section 9.2.1) will be used at the discretion of the usual care provider (or Investigator if also the usual care provider). Relevant information about all concomitant medications (including prescribed, over-the-counter, or herbal preparations) taken prior to (ie, within 30 days of Screening) and during the study must be recorded in the source documents and CRF, as well as any dose or dose regimen changes that occur during the study. Concomitant medications should be stable prior to Day 0.

Drug Interactions

Subjects taking bile acid sequestrants (BAS, including cholestyramine and its derivatives, colestipol, colesevelam, or other sequestrants) or aluminum hydroxide- or smectite-containing antacids should be instructed to stagger their dosing of investigational product and UDCA, ensuring at least 4 hours between doses of the BAS and/or these antacids and the investigational product (and UDCA; ie, BAS should be administered at minimum 4 hours before or 4 hours after investigational product administration).

OCA taken concomitantly with warfarin may result in decreased INR levels, therefore, INR should be monitored and the dosage of warfarin adjusted, as needed during treatment with OCA and after cessation of OCA, to maintain the target INR range.

The effect of OCA on drug metabolizing enzymes has been evaluated in both in vitro and clinical studies. The PK profile of caffeine, a sensitive CYP1A2 substrate probe, showed weak effect of OCA on CYP1A2. Based on these results, OCA may increase the exposure of narrow therapeutic index drugs that are substrates for CYP1A2, such as theophylline and tizanidine.

Information related to additional drug-drug interaction (DDI) studies is available in the current version of the Investigator's Brochure (IB). The aforementioned sections of the IB should be referred to during the course of the study, and are accessible to investigators to help facilitate the assessment of potential drug-drug interactions with OCA that may be observed in study subjects.

PBC Specific Therapy

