9.2.1. Prohibited Medications

Commercial OCA therapy (if available) is prohibited while on investigational product, and if prescribed during the course of the study, the Investigator should be cognizant of the possibility of double dosing. Subjects who continue with commercial OCA therapy must discontinue study

medication and are expected to continue through the end of the study (see [Section 7.4.2](#)). The study will only terminate at the time when the needed number of adjudicated events has accrued or at the discretion of the Sponsor. Subjects will need to complete EOT procedures but continue with regularly scheduled visits until the study is terminated (see [Section 9.7.18](#) Early Discontinuation and/or Early Termination Procedures).

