9.7. Visit Procedures

9.7.1. Visit Windows

Visits should be based on Day 0 (not on the prior visit), eg, Month 3 should ideally occur 3 calendar months (± 2 weeks) following Day 0. The visit windows are as follows:

Visit or Procedure	Visit Window and/or Interval
Screening	Screening Visit 1 interval is 3 to 8 weeks prior to Day 0. Screening Visit 2 interval is 1 to 6 weeks prior to Day 0. The visit window for Screening 2 visits allows for the repeat biochemistry tests to be collected at least two weeks after the initial biochemistry sample was collected and will ensure ample time to receive lab results. The overall Screening interval is up to 56 days, but screening procedures should not be performed during the last 7 days of the window.
Day 0	This is the day of randomization. On-treatment visit scheduling should be calculated from this point going forward. (The first dose of investigational product should be taken the next day, on Day 1.)
Month 1	+1 week (7 days)
Titration Visit – Standard Dosing Regimen	\geq Month 3
Titration Visit 1 – Modified Dosing Regimen	\geq Month 3
Titration Visit 2 – Modified Dosing Regimen	\geq 6 weeks after Titration Visit 1
Titration Visit 3 – Modified Dosing Regimen (Child-Pugh B ONLY)	\geq 6 weeks after Titration Visit 2
Post-Titration Visit	1 month (+1 week [7 days]) from date of titration or after \geq 3 months at a decreased dose or frequency
Month 3 to Month 12	\pm 2 weeks (14 days)
Quarterly visits (Months 15 to EOS)	\pm 2 weeks (14 days)
EOT (When subject discontinues investigational product)	As soon as possible upon study discontinuation and as near as possible to last dose taken
EOS (When subject terminates the study)	The final study visit; EOS will occur concurrent with EOT if a subject discontinues study medication at the time the subject's participation in the study ends (eg, withdrawal of consent or study termination by the Sponsor); EOS will occur after the EOT if the subject discontinues study medication but continues in the study.

EOS = end of study; EOT = end of treatment

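### The OCA washout at entry covers only earlier OCA studies, so a current user of commercial OCA can be randomized with on-drug screening and baseline values

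*Protocol*

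**What the plan says.** All references are to the current protocol, Version 3.

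- **Section 8.3, exclusion 11:** "Participation in a previous study of OCA is allowed with 3 months washout prior to enrollment in this study". The synopsis has the same rule. The first sentence of the criterion sets a 30-day gap from any other investigational study, counted back from Screening.
- **Section 5.1:** the FDA "has granted accelerated approval for Ocaliva for the treatment of PBC". Section 5.5.2.1 gives the commercial doses as 5 mg and 10 mg, the same strengths as the study tablets.
- **Section 9.2.1:** "Commercial OCA therapy (if available) is prohibited while on investigational product". A subject who continues commercial OCA must stop study medication but stays in follow-up.
- **Section 9.7.1:** randomization is on Day 0. "The first dose of investigational product should be taken the next day, on Day 1".
- **Section 9.2:** "Concomitant medications should be stable prior to Day 0".
- **Section 8.2, inclusion 4, for comparison:** UDCA has an explicit entry rule, beginning "Either is not taking UDCA (no UDCA dose in the past 3 months", or else at least 12 months of use with a stable dose for at least 3 months.

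No inclusion or exclusion criterion names commercial OCA.

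**The concern.** The protocol accepts that earlier OCA needs a washout before entry, but ties the washout to where the drug came from. A former trial participant must wait 3 months. A patient who takes the same drug on prescription has no stated wait. The other provisions on commercial OCA (sections 8.4.2 and 9.2.1, the note to Table 7, and the bias remark in section 5.5.2.3) deal with starting or continuing it after entry.

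Three uses of the laboratory values are exposed:

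- The means of the screening ALP and bilirubin decide eligibility (section 9.7.6).
- Mean bilirubin sets the randomization stratum (section 9.4).
- Baseline values enter the analyses of change in total bilirubin and ALP, steps 4 and 5 of the testing sequence (sections 13.1.4 and 13.1.11).

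For a subject who stops OCA just before the first dose, these values reflect the study drug. The randomized contrast in that subject is continuing against stopping OCA, whereas the trial asks about adding OCA against not adding it.

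**Working it through.** **1. Reading the rules together.** Take a patient on prescribed OCA throughout screening who stops on the day before Day 0.

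| Rule | Does it bar randomization? |
|---|---|
| Exclusion 11 | No: applies to previous OCA studies |
| Other criteria in 8.2 and 8.3 | No: none names commercial OCA |
| 9.2.1 prohibition | No: starts with investigational product, on Day 1 |
| 9.2 stability sentence | No: gives no drug and no duration, and is not an eligibility criterion |
| Day 0 plasma OCA sample (9.7.7) | No: not used for eligibility |

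The patient must still meet inclusion 2 (bilirubin above ULN and up to 3 times ULN, and/or ALP above 5 times ULN), here on OCA.

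**2. ALP change in one such subject.** The plan states no figure on this point, and the 121-event target does not depend on it. Section 5.4 supplies the inputs:

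- Study 747-301: mean ALP falls of 33% (titration) and 39% (10 mg) on OCA, and 5% on placebo.
- Study 747-202, on stable UDCA: falls of 21% to 25% on OCA, and 3% on placebo.

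Assumption: the OCA effect reverses fully off drug. With an on-OCA baseline,

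change on placebo = (1 - placebo fall) / (1 - OCA fall) - 1; change on continued OCA ≈ 0.

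- 747-301: 0.95/0.67 - 1 = +42%; 0.95/0.61 - 1 = +56%.
- 747-202: 0.97/0.79 - 1 = +23%; 0.97/0.75 - 1 = +29%.

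Without prior OCA, the placebo change would be -5% or -3%.

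**3. Effect on the arm means.** The share f of such subjects is not in the documents, so it is assumed. Using the largest effect (39% on OCA, 5% on placebo):

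placebo mean = (1 - f)(-5) + f(+55.7); OCA mean = (1 - f)(-39) + f(0).

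| f | Placebo | OCA | Difference (points) |
|---|---|---|---|
| 0% | -5.0 | -39.0 | -34.0 |
| 5% | -2.0 | -37.0 | -35.1 |
| 10% | +1.1 | -35.1 | -36.2 |
| 20% | +7.1 | -31.2 | -38.3 |

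Both arm means rise, so the difference moves less: 1.1 points at 5% and 2.2 points at 10%.

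**4. The reference point of the washout.** Screening Visit 1 is 3 to 8 weeks before Day 0. If enrollment means Day 0 and 3 months is taken as 13 weeks, a compliant former trial participant can have the first eligibility sample 13 - 8 = 5 to 13 - 3 = 10 weeks after the last OCA dose. The 30-day rule in the same criterion runs to Screening and leaves no such overlap.

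**The case against.** Other text speaks against the scenario. Section 9.2 expects concomitant medication to be stable before Day 0 and would ideally keep subjects on their baseline PBC treatment, so stopping a PBC drug the day before randomization fits neither. An investigator could decline the patient on that ground. These are soft expectations, however, and a commercial OCA user cannot both stay on that therapy and comply with section 9.2.1. The gap stays open.

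The scale is limited, and this part of the objection stands. Section 5.1 limits approval to the US. Such subjects must qualify on bilirubin or ALP while taking OCA. Randomization spreads them over both arms, and the ANCOVA adjusts for baseline. That adjustment uses the baseline level, though, and cannot tell a value lowered by OCA from the same value off drug.

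Four stronger inferences are tempting but not supported:

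- **Earlier commercial use goes unrecorded.** The 30-day limit ("taken prior to (ie, within 30 days of Screening") applies to the concomitant-medication record. PBC treatment history is also collected at Screening (sections 9.7.6 and 12.2.6).
- **The placebo arm as a whole becomes a withdrawal arm.** This applies only to the affected subjects.
- **Subjects continuing on OCA were selected for tolerating it.** A patient leaving commercial OCA may equally have tolerated it badly or not responded.
- **An OCA effect is known to persist at the first screening sample after a study washout.** Nothing in the document shows an effect at 5 weeks.

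**Conclusion.** The gap is real: an entry rule is stated with too narrow a scope, and its reference point differs from that of its neighbour in the same criterion. For the affected subjects, the eligibility values, stratum and baseline are measured on OCA or just after it, and the randomized comparison is continuation against withdrawal.

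The consequence is for what is estimated and for the change-from-baseline results. Type I error is not inflated. Under full reversal, the ALP change in an affected placebo subject is about +23% to +56%, and the between-arm difference shifts by about 1 to 2 points at an assumed share of 5% to 10%. The share is unknown, and the reversal is an assumption. The documents give no basis for quantifying an effect on the primary time-to-event result, and none is claimed. The change is worth making because it is cheap, not because the trial's conclusion hangs on it.

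**What to change.** Reconcile exclusion 11, in section 8.3 and the synopsis, with section 9.2.1, so that one entry rule covers all prior OCA, whether from a study or a prescription. State in that rule whether the interval is counted back to Screening, where the eligibility samples are drawn, or to Day 0. The length of the interval is for the sponsor to set.

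The cost is one sentence in the next protocol version. Some users of commercial OCA would become ineligible or enter later, which matters in a rare disease, although the number is probably small. If the interval is counted to Screening, former trial participants would also be off OCA for longer before randomization. The sponsor should weigh this when choosing the reference visit.

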8.4. Subject Withdrawal from Investigational Product or Study

8.4.1. Reasons for Mandatory Discontinuation of Investigational Product

If a female subject becomes pregnant, she must discontinue taking investigational product, but should continue with the study visit schedule. The subject must be followed as considered appropriate by the Investigator and the medical monitor through pregnancy outcome. For reporting purposes pregnancy is not considered an AE. The subject may reinstate investigational product after delivery and cessation of breastfeeding (if applicable) at the discretion of the Investigator. Subjects whose pregnancy is terminated early (planned or unplanned) may be permitted to resume participation in the study if termination of the pregnancy is confirmed by a serum beta human chorionic gonadotropin (β -hCG) test performed at the central laboratory.

8.4.2. Other Reasons for Discontinuation of Study or Investigational Product

Subjects that discontinue investigational product are expected to continue in the study until the end of the study, and the study will only terminate at the time when the needed number of adjudicated events has accrued or at the discretion of the Sponsor. If a subject reaches an event, he or she should continue the regular visit schedule and continue taking investigational product as long as the Investigator assesses it as safe. Subjects who choose to discontinue investigational product prior to termination of the study need to also continue to follow the regular visit schedule

through to study closure. In general, subjects should be strongly encouraged to both stay on investigational product and remain in the study until study termination. Early termination procedures should only be conducted if the subject withdraws consent (See [Section 9.7.18](#) Early Discontinuation and/or Early Termination Procedures).

The following events are considered appropriate reasons for a subject to discontinue investigational product; however, these subjects are expected to continue in the study until study termination and the study will only terminate at the time when the needed number of adjudicated events has accrued (or at the discretion of the Sponsor):

- Subject begins treatment with commercially available OCA
- The Investigator or Sponsor considers that it is advisable or in the best interest of the subject.
- The occurrence of clinical or laboratory AEs considered by the Investigator to be clinically important safety concerns and related to study drug.
- Withdrawal of consent
 - Consent may be fully withdrawn (in which case the subject discontinues both investigational product and study visits and procedures).
 - Consent may be modified to discontinue study visits but allow semi-annual telephone contact.
 - Consent may be modified to discontinue study visits or semi-annual telephone contact but allow continued access to medical records to assess for potential adjudicated hepatic and/or cardiovascular events.

Subjects who undergo a liver transplant during the course of the study must discontinue investigational product and discontinue the study visit schedule. However, these subjects should be encouraged to consent to the semiannual telephone contact and/or continued record review only to allow for secondary outcome events data to be collected.

The Investigator must notify the Sponsor study monitor by telephone or email as soon as possible if any subject prematurely withdraws from the study.

